Tranexamic acid's role in treating hemorrhage have been widely studied in non-pregnant populations. Studies of TXA in obstetrics are limited. The American College of Obstetricians and Gynecologists believes the data is insufficient to recommend tranexamic acid for prophylaxis⁹.

We designed a randomized placebo-controlled trial comparing TXA dosing prior to incision for cesarean delivery with a repeat dose given at placental delivery. Our purpose is to quantify blood loss during uncomplicated repeat cesarean deliveries with and without TXA. We elected to study scheduled elective cesareans because such procedures are at low risk for profound hemorrhage. It is our intent to have a study cohort where the two treatment groups (TXA or placebo) are as comparable as possible, so we are not testing the efficacy of TXA in women with highly variable volumes of obstetric hemorrhage. TXA here-to-for has not been studied in a context where blood volume loss was quantified in both study groups.

Specific Aims:

Specific Aim 1: To determine the efficacy of perioperative TXA administration on reducing blood loss in women undergoing scheduled repeat cesarean delivery. We will use a method for calculating blood loss previously described by our group in an observational study of 1443 women with obstetrical hemorrhage¹⁰. Using this mathematical method to calculate maternal blood volume, pre- and post-cesarean, we hypothesize that an initial bolus of TXA with a second bolus at placental delivery will reduce blood loss in comparison to placebo.

Specific Aim 2a: To quantify maternal fibrinolytic activity with and without TXA in women undergoing cesarean delivery. In vitro serum markers of fibrinolysis (fibrinogen, plasminogen activator inhibitor-1 (PAI-1), tissue plasminogen activator (t-PA), and D-dimer) and rotational thromboelastometry will be used to quantify fibrinolytic activity. Given that TXA is a lysine analog that prevents the conversion of plasminogen to plasmin, thereby inhibiting fibrinolysis⁶, we *hypothesize* that in women given TXA, will have less evidence of fibrinolysis on measurement of serum markers and rotational thromboelastometry¹¹.

Specific Aim 2b: To ascertain if TXA effects on fibrinolysis dissipate by postoperative day

1. We *hypothesize* that by postoperative day 1, effects of TXA will have dissipated, as evidenced by comparable levels of fibrinolysis (serum markers and rotational thromboelastometry) in the TXA and placebo groups.

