Concise Summary of Project:

This is the first trial to utilize a regimen of TXA that uses a prophylactic dose of TXA prior to incision followed by a subsequent prophylactic dose at placental delivery in obstetric patients undergoing scheduled cesareans. The outcome of interest is quantified blood loss.

We prepared a novel study of TXA designed to estimate the quantity of blood loss in women undergoing repeat cesareans. This group was chosen to minimize the large variability of hemorrhage in women after extreme hemorrhage has already commenced.

We are of the belief that careful study of TXA is imperative in any material or state level effort to mitigate obstetric hemorrhage's¹² impact on maternal health. If TXA is shown to quantitatively reduce obstetric hemorrhage in the highly controlled trial we now propose, then subsequent trials can be designed to test not only prophylaxis, but adjunct TXA therapy in the setting of ongoing severe maternal hemorrhage.

The training and research activities described in this application will occur in coordination with the Departments of Anesthesiology, and Obstetrics and Gynecology. Parkland Hospital is conducive to such a study because of a large delivery volume of >12,000 per year as well as a nationally recognized service.

Study Procedures: *Study Design*

This is a double-blind, randomized, placebo-controlled trial designed to assess the superiority of a prophylactic dose of TXA prior to skin incision with a repeated bolus at placental delivery compared to placebo. The outcome of interest is a reduction in blood loss in comparable women undergoing routine scheduled cesarean delivery. Women that meet inclusion criteria will be approached for informed consent [Table 1]. After written informed consent and HIPAA authorization is obtained, participants will be randomized to either 1) placebo-group: normal saline or 2) treatment group: TXA. Figure 3 illustrates the participant flow from screening through completion of this study.

Table 1 Inclusion/Exclusion Criteria.

Inclusion Criteria	Exclusion Criteria

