Figure 3 Timeline of data collection and outcomes of interest
Markers of fibrinolysis: tissue plasminogen activator, plasminogen activator inhibitor-1, D-Dimer & fibrinogen level

AIM-SPECIFIC APPROACH

Aim 1: To determine the efficacy of perioperative TXA administration on reducing blood loss in women undergoing scheduled repeat cesarean delivery.

Method: In each study group, we will calculate total blood volume lost using the mathematical method described in **Table 2**¹⁰.

Table 2 Mathematical method for calculating total blood volume loss.

HCT: hematocrit; RBC: red blood cell

^a Assumptions for transfused blood: (1) packed red blood cells contains 330 mL total volume with HCT 55 vol% or 182 mL RBC volume per unit; (2) whole blood contains 450 mL total volume with HCT 40 vol% or 180 mL RBC volume per unit.

Method for Calculation of Total Blood Volume Lost Due to Obstetric Hemorrhage	
Step 1	Calculate total non-pregnant blood volume: $[(\text{height in inches} \times 50) + (\text{weight in pounds} \times 25)] \div 2$
Step 2	Add 50% for average pregnancy volume expansion (i.e., hypervolemia of pregnancy)
Step 3	Pregnancy total blood volume \times admission HCT (vol %) = admission RBC volume
Step 4	Assume total blood volume has returned at discharge to the non-pregnant total blood volume as a result of hemorrhage. Therefore, non-pregnant blood volume \times discharge HCT (vol%) = discharge RBC volume
Step 5	Calculate total blood volume lost: $(\text{admission RBC volume} - \text{discharge RBC vol \%} + \text{RBC volume transfused}^a) \div \text{admission HCT (vol \%)}$

Specific Aim 2a: To quantify maternal fibrinolytic activity with and without TXA in women undergoing cesarean delivery. In vitro serum markers of fibrinolysis (fibrinogen, plasminogen activator inhibitor-1 (PAI-1), tissue plasminogen activator (t-PA), and D-dimer) and rotational thromboelastometry will be used to quantify fibrinolytic activity.

Specific Aim 2b: To ascertain if TXA effects on fibrinolysis dissipate by postoperative day 1.

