Methods: For plasma *in-vitro* fibrinolytic activity (To be collected before initiation of infusion of TXA or placebo, at placental delivery, and on postpartum day 1): quantitative t-PA and PAI-1 levels will be collected in a light blue top container with 3.2% sodium citrate. The specimens will be transported to the research lab, stored at -20°C, and batch testing performed when appropriate. Fibrinogen levels and D-Dimer will be collected in a blue top container with 3.2% sodium citrate. The specimen for hematocrit will be collected in a lavender container.

For rotational thromboelastometry (ROTEM™), (To be collected before initiation of infusion, TXA or placebo, at delivery, and on postpartum day one): a small aliquot of venous blood will be added to a disposable cuvette (measuring cell) in a heated cuvette holder. A disposable pin (sensor) fixed to a rotating shaft rotates back and forth 4.75 degrees. The exact position of the shaft is detected by reflection of light on a small mirror on the shaft. Data obtained from the reflected light is then computer processed into a graphical output with numerical values reported.

On ROTEM™ analysis, we will compare ML values at 60 minutes, CT, CFT, and MCF values, numerically and graphically. Normal levels are graphically depicted in **Fig. 4**, fibrinogen deficiency in **Fig. 5**, and hyperfibrinolysis in **Fig. 6**.

[figure not shown]

Fig. 4. Normal levels on ROTEM™.

[figure not shown]

Fig 5. Fibrinogen deficiency on ROTEM™.

[figure not shown]

Fig. 6 Hyperfibrinolysis on ROTEM™.

Sources of Research Material: There are two electronic data sets to be used in this proposed study:

- 1) The Epic Electronic Medical Record (EMR) system at Parkland Hospital provides an integrated EMR system. Patient data is entered through a menu driven, formatted data entry screen and may be reviewed through similar processes. It was implemented at Parkland April 28, 2009. Epic is managed by Information Technology at Parkland and maintains strong security.

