## **Statistical Analysis Plan**

Sample Size (total sample size=100, power 0.80, two-sided)

We selected a pilot of 20 patients randomly from schedule cesarean deliveries at Parkland Hospital. For this sample we performed the blood loss calculation for each delivery. This resulted in a mean blood loss of 2224 mL and a standard deviation of 362 mL. The trial is designed to observe a 205 mL reduction in the TXA arm over the placebo arms as from 2224 mL (placebo arm) to 2019 mL (TXA arm) with 80% power. This requires fifty patients randomized to each arm (one hundred total patients) using a two-sided test of significance level 0.05 using a Student's t-test.

Randomization was performed using a computer-generated table provided to the investigational drug pharmacy before patient recruitment. Randomization was according to randomized permuted blocks of size 6, 8, and 10. Data analysis included Pearson  $\chi^2$  for categorical data and Student's t-test for continuous data. P-values <0.05 were considered significant. Analyses were conducted with SAS version 4.1 (SAS Institute, Cary, NC).

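### Aim 2b predicts comparable arms on postoperative day 1, but the plan sets no criterion for comparability and its only inferential rule, a t-test at p<0.05, cannot show it

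*Protocol*

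**What the plan says.** The protocol's Specific Aims section states Aim 2b as a hypothesis of no difference: TXA effects will have gone by postoperative day 1, "evidenced by comparable levels of fibrinolysis (serum markers and rotational thromboelastometry) in the TXA and placebo groups". The Aim-Specific Approach repeats the aim, "To ascertain if TXA effects on fibrinolysis dissipate by postoperative day 1", and adds no criterion.

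The Methods text under that heading gives the sampling times: "To be collected before initiation of infusion of TXA or placebo, at placental delivery, and on postpartum day 1". For ROTEM it says "we will compare ML values at 60 minutes, CT, CFT, and MCF values, numerically and graphically", with no threshold. That makes eight possible read-outs: four serum markers (fibrinogen, PAI-1, t-PA, D-dimer) and four ROTEM values (ML, CT, CFT, MCF).

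The Study Design section describes a trial "designed to assess the superiority of a prophylactic dose of TXA prior to skin incision". The SAP names "Student's t-test for continuous data" and adds that "P-values <0.05 were considered significant". It also names Pearson's chi-square, which does not apply to these continuous measurements.

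In the text available, neither document gives a margin for comparability, a confidence-interval rule, a way to combine the read-outs, or a sample size for Aim 2b. One part of the SAP file was not available for review.

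**The concern.** A superiority t-test can reject equality of the arms, but failing to reject does not establish it. With a moderate sample, p≥0.05 is common even when a real difference remains. Aim 2b needs a positive statement that the arms are close, and the plan supplies no tool for making one. The documents do not say that p≥0.05 will count as dissipation, but they offer no other criterion.

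Two things are at stake. A non-significant day-1 result could be reported as dissipation while the data remain compatible with a sizeable residual effect. And with up to eight read-outs and no combining rule, what counts as comparable overall can be settled after the data are seen.

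**Working it through.** **Inputs.** From the documents: 50 per arm, two-sided alpha 0.05, Student's t-test, and for blood loss a difference of 205 mL with SD 362 mL. Assumed, because the documents give no values: true day-1 differences in SD units, 40 day-1 samples per arm as a loss scenario, the correlations, and the margins.

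**1. The plan's own figure.** The standardized blood-loss effect is 205/362 = 0.566. The normal approximation gives 2 × (1.960 + 0.842)² / 0.566² ≈ 49 per arm. The exact noncentral-t power is 0.792 at 49 and 0.801 at 50 per arm. The stated 50 per arm reproduces and is not in question. It is the only power statement in the plan and concerns blood loss alone.

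**2. Chance of p≥0.05 when a difference d (in SDs) remains, one marker.** The t statistic has noncentrality d × √(n/2) on 2n − 2 degrees of freedom. At n = 50 this is 5d on 98 df.

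| True day-1 difference | 50 per arm | 40 per arm (assumed) |
|---|---|---|
| 0.2 SD | 83% | 86% |
| 0.3 SD | 68% | 74% |
| 0.4 SD | 49% | 58% |
| 0.5 SD | 30% | 40% |

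**3. Precision.** The 95% half-width is t(0.975, 98) × √(2/50) = 1.984 × 0.2 = 0.397 SD (0.445 SD at 40 per arm). A result just at p=0.05 has an interval from 0 to 2 × 0.397 = 0.794 SD. An estimate of exactly zero excludes only differences beyond about 0.40 SD. The 90% half-width is 1.661 × 0.2 = 0.332 SD.

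**4. Eight read-outs together.** Suppose comparability meant that all eight were non-significant.
- Each truly differs by 0.3 SD: the probability is 0.682⁸ = 0.047 if they are independent, 0.26 at inter-marker correlation 0.5 (simulated), and 0.682 if perfectly correlated.
- None differs: 0.95⁸ = 0.663 if independent, up to 0.95 if perfectly correlated.

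The plan does not propose this rule. The spread shows how far an overall answer depends on a rule it leaves unstated.

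**5. Gain from baseline adjustment.** Adjusting for the pre-infusion value multiplies the half-width by √(1 − ρ²), on 97 df. The 95% half-width becomes 0.379, 0.344 or 0.283 SD at ρ = 0.3, 0.5 or 0.7. The 90% half-width at ρ = 0.5 is 0.288 SD.

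**6. What a margin-based rule could achieve at 50 per arm.** The rule is that the 90% CI lies inside ±margin. With a true difference of zero and no adjustment, it is met with this probability:

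| Margin | Probability of meeting it |
|---|---|
| 0.3 SD | 0.4% (7.5% with adjustment at ρ = 0.5) |
| 0.4 SD | 27% |
| 0.5 SD | 60% |
| 0.6 SD | 82% |

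The smallest margin with 80% power is about 0.59 SD per marker, unadjusted. A 0.3 SD margin would need 191 per arm for 80% power.

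**The case against.** The strongest reply is that the harm is hypothetical. The plan never says a non-significant result will be read as dissipation, the restated aim is neutral, and the ROTEM comparison is already partly descriptive. The t-test is also informative: it can refute dissipation, and at 50 per arm it would miss a true 1.0 SD difference only about 0.1% of the time. Samples at three times add context, since an arm difference at placental delivery that is absent on day 1 would be relevant evidence. Finally, the sizes above rest on assumed differences and correlations, and the all-eight rule is not the sponsor's.

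Much of this is fair. The SD-unit figures are illustrations, 0.79 SD is the extreme case of a result exactly at p=0.05, and large residual effects would be detected. But the power to refute dissipation is not the power to confirm comparability, and Aim 2b predicts comparability. A significant difference at delivery followed by a non-significant one on day 1 is not a test that the effect has gone. Describing ROTEM values numerically and graphically sets no criterion and does not cover the serum markers.

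**Conclusion.** The concern holds. As written, the plan leaves non-significance as the only formal basis for an Aim 2b conclusion, and that basis cannot exclude small-to-moderate residual differences. At 50 per arm with one marker, true differences of 0.3 to 0.5 SD would go undetected 68% to 30% of the time, and the 95% CI extends about 0.40 SD either side of the estimate. These figures follow from the planned sample size and alpha; the differences are assumed, because no marker SDs or margins are given.

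The consequence is limited to a mechanistic aim. Aim 1 and the total of 100 women are unaffected. The SAP should still be changed, because the remedy is cheap and uses data already planned.

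**What to change.** In the SAP, replace the t-test as the analysis for Aim 2b with the following.

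- For each serum marker and ROTEM value, estimate the day-1 between-arm difference, adjusted for the pre-infusion value, and report it with its 95% CI.
- State that p≥0.05 is not evidence of comparability, and treat Aim 2b as descriptive, reported marker by marker.
- Conclude that the effect has dissipated for a marker only if a margin was specified in advance, was justified for that marker and not chosen because 50 per arm can power it, and contains the whole 90% CI.
- If an overall statement is wanted, name in advance the markers that must meet the criterion.

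The cost is SAP wording and a different read-out of samples already planned, with no extra patients or assays. The downside is that some or all markers may be reported as inconclusive. A margin as tight as 0.3 SD would almost never be met at this sample size, which is why estimation is the realistic default.

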- 2) Selected obstetrical outcomes for all women who give birth at Parkland Hospital, as well as neonatal outcomes, are entered into a computerized obstetric database. Nurses attending each delivery complete an obstetrical data sheet, and research nurses assess the data for consistency and completeness before they are stored electronically. Data on neonatal outcomes are abstracted from discharge records. These data are stored on a secure file server maintained by the Department of Obstetrics and Gynecology.

Recruitment Methods and Consenting Process: Women scheduled for elective cesarean delivery Monday through Friday at Parkland Labor and Delivery and who meet the inclusion criteria will be eligible to participate. A research nurse will screen all women that meet study criteria. After identification of a potential subject, the principal investigator will discuss the research protocol, answer any questions, and obtain consent and HIPAA authorization. Consents will be available in English and Spanish, and an interpreter will be available.

Potential Risks:

	Frequent (30% of subjects)	Uncommon (<15% of subjects)
Major		Tranexamic acid: 
 • Hypotension (rare) • Thromboembolism (Maternal AND fetal) (rare) • Seizures (rare) • Anaphylaxis (rare) Venous blood draw: 
 • Excessive bleeding (rare) • Infection (rare) • Fainting (rare)
Minor		Tranexamic Acid: 
 • Stomach discomfort • Nasal congestion • Headache • Joint and Muscle Pain • Vision changes Venous blood draw: 
 • Discomfort at the needle site • Bruising • Clotting

Subject Safety and Data Monitoring:

Human Subjects Involvement and Characteristics:

We are proposing to enroll a total of 100 women into two study arms of 50 women each. Enrollment will be done exclusively at Parkland Hospital. Women who present for cesarean delivery will be screened by study team for eligibility. All women who volunteer to participate will sign a UTSW IRB-approved consent form and HIPAA authorization. Before being transported to the operating room, blood will be obtained by the study team for hematocrit (routine care), markers of fibrinolysis, & ROTEM analysis. The study team will then order “study drug” to be given:

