- 1) TXA 1 gram (diluted in 100 mL normal saline) given intravenously over 10 minutes, 10 minutes before skin incision *followed by* TXA 1 gram (diluted in 100 mL normal saline) given intravenously over 10 minutes at time of placental delivery.
- 2) Placebo (100 mL of normal saline) given intravenously over 10 minutes, 10 minutes before skin incision *followed by* placebo (100 mL normal saline) given intravenously over 10 minutes at time of placental delivery.

Parkland's *Investigational Drug Pharmacy* will prepare a blinded solution containing TXA or saline with a unique identifier according to a computerized randomization allocation sequence generated by [name] (statistician). The pharmacist on-call will deliver the solutions to an attending anesthesiologist. The study team which includes a research nurse will ensure that the solutions are infused per protocol. At delivery of the placenta & on postoperative day # 1, blood will be drawn for analysis of hematocrit, markers of fibrinolysis, & ROTEM by a study team member.

Sources of Materials:

Each participant will be assigned a unique study ID at enrollment. Blood samples collected from each participant will be appropriately labeled with the study ID number and will not contain patient identifiers. A master list linking the study ID with subject's information will be maintained by [name] on a secure, password-protected computer in his locked office with automatic saving to a secure, password-protected, backup hard drive. A Microsoft Access® database containing the collected information will be maintained separately on a secure, password-protected server that is accessible only within the University of Texas Southwestern. The database will not include protected health-care information. All information and material will be obtained for research purposes only and kept in strictly confidential. Any paper documents resulting from the study are kept in locked file cabinets accessible only by authorized research personnel.

Research material will include a total of 36 mL of **maternal** venous blood (twelve mL x three collections) and clinical information. Clinical information will be collected from the electronic medical record and direct patient interview. Collected information includes demographic information, medical and surgical history, physical examination, laboratory, imaging, and pathology reports.

Potential Risks:

The potential **maternal** risks involved in this study include:

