A data and safety monitoring board assembled of diverse specialists including [name] Obstetrics, [name] and [name] Anesthesiology will meet quarterly to monitor for protocol adherence and adverse events. [name], Biostatistician, will lead this board.

BIOSTATISTICS

Sample Size (total sample size=100, power 0.80, two-sided)

We selected a pilot of 20 patients randomly from schedule cesarean deliveries at Parkland Hospital. For this sample we performed the blood loss calculation for each delivery. This resulted in a mean blood loss of 2224 mL and a standard deviation of 362 mL. The trial is designed to observe a 205 mL reduction in the TXA arm over the placebo arms as from 2224 mL (placebo arm) to 2019 mL (TXA arm) with 80% power. This requires fifty patients randomized to each arm (one hundred total patients) using a two-sided test of significance level 0.05 using a Student's t-test.

Bibliography

1. Science JMECfCDaC. *Management of postpartum hemorrhage: current state of the evidence*. Rockville (MD): Agency for Healthcare Research and Quality; 2016.
2. B F, Awolude O, Adeniji A, Onafowokan O. *WHO Recommendations for the Prevention of Postpartum Haemorrhage. Making Pregnancy Safer*. 2010.
6. McCormack PL. Tranexamic acid: a review of its use in the treatment of hyperfibrinolysis. *Drugs*. 2012;72(5):585-617.
7. collaborators C-t, Shakur H, Roberts I, et al. Effects of tranexamic acid on death, vascular occlusive events, and blood transfusion in trauma patients with significant haemorrhage (CRASH-2): a randomised, placebo-controlled trial. *Lancet*. 2010;376(9734):23-32.
8. Collaborators WT. Effect of early tranexamic acid administration on mortality, hysterectomy, and other morbidities in women with post-partum haemorrhage (WOMAN): an international, randomised, double-blind, placebo-controlled trial. *Lancet*. 2017;389(10084):2105-2116.
9. Committee on Practice B-O. Practice Bulletin No. 183: Postpartum Hemorrhage. *Obstet Gynecol*. 2017;130(4):e168-e186.

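### Does the discharge hematocrit in Table 2 undermine the Aim 1 outcome, when the last scheduled draw is on postoperative day 1?

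*Protocol*

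**What the plan says.** The Protocol defines the outcome in Table 2 (Aim-Specific Approach, Aim 1). Step 4 closes the calculation with "discharge HCT (vol%) = discharge RBC volume" and gives the volume it relies on: "Assume total blood volume has returned at discharge to the non-pregnant total blood volume as a result of hemorrhage". Specific Aim 1 describes the comparison only as before and after the cesarean.

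The draws are set out elsewhere in the Protocol. Under Human Subjects Involvement and Characteristics, the baseline sample is described thus: "Before being transported to the operating room, blood will be obtained by the study team for hematocrit (routine care". The later samples are at delivery of the placenta and then "on postoperative day # 1, blood will be drawn for analysis of hematocrit, markers of fibrinolysis, & ROTEM by a study team member". The Methods for Aims 2a and 2b give the same three times ("To be collected before initiation of infusion of TXA or placebo, at placental delivery, and on postpartum day 1") and add that "The specimen for hematocrit will be collected in a lavender container". Sources of Materials counts three collections in all. It also lists chart data, including "physical examination, laboratory, imaging, and pathology reports", without naming a hematocrit.

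On planning, the Protocol (Biostatistics) and the SAP both state: "We selected a pilot of 20 patients randomly from schedule cesarean deliveries at Parkland Hospital". The loss was calculated for each of these women, with mean 2224 mL and SD 362 mL. Neither document gives the timing of the hematocrit behind those figures, and the readable SAP does not define the closing hematocrit.

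**The concern.** The value that carries Step 4's volume assumption has no scheduled draw, and the value that has a scheduled draw is not the one for which the assumption is stated. Two sources seem open: the day 1 study sample, or a later value from the chart. The pilot women were not on the trial's draw schedule, so their closing value presumably came from the chart.

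This is the only outcome with a power calculation. If the closing value were drawn from different days in different women, the added spread would cost power in a design with almost no reserve. A reader could not recompute the result exactly, or confirm that the planning SD belongs to the outcome being analysed.

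**Working it through.** **Planned sample size.** Inputs from the Protocol (Biostatistics) and the SAP: difference 205 mL, SD 362 mL, two-sided 0.05, 80% power.

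- Normal approximation: n = 2 × (1.960 + 0.842)² × 362² / 205² = 48.9, so 49 per arm.
- Two-sample t-test (noncentral t): n = 49.93, so 50 per arm. Power at 50 per arm is 80.1%.

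The stated 50 per arm reproduces, and the hematocrit question does not enter this arithmetic.

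**Sensitivity to the closing hematocrit.** Let V be the non-pregnant volume (Step 1), Ha the admission hematocrit, Hp the closing hematocrit and T the transfused red-cell volume. Steps 2 to 5 give

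L = (1.5·V·Ha − V·Hp + T) / Ha = V(1.5 − Hp/Ha) + T/Ha.

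One point of Hp therefore moves L by V/Ha. The documents give neither V nor Ha. The assumed values are V = 3400 to 4200 mL and Ha = 35%.

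| V (mL) | mL per point (V/35) | Points equal to 205 mL |
|---|---|---|
| 3400 | 97.1 | 2.11 |
| 3800 | 108.6 | 1.89 |
| 4200 | 120.0 | 1.71 |

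**Case 1: one time point for all women.** A later draw that differs by d points in both arms changes each arm's mean loss by d × V/35. For d = 1 to 2 that is 97 to 240 mL. Randomization makes the expected change the same in both arms, so the difference between arms is unaffected. A constant shift of this kind adds no variance and costs no power.

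**Case 2: time points mixed across women.** If a fraction p has a value shifted by d points, the added SD is d × √(p(1 − p)) × V/35. This combines with 362 mL in quadrature.

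- Mildest corner (V 3400, d = 1, p = 0.2): added SD 1 × 0.4 × 97.1 = 38.9 mL. Total √(362² + 38.9²) = 364.1 mL, power 79.6%.
- Worst corner (V 4200, d = 2, p = 0.5): added SD 2 × 0.5 × 120 = 120 mL. Total √(362² + 120²) = 381.4 mL, power 75.8%.

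Both p and d are assumed, and nothing in the documents indicates mixing. If the pilot charts themselves mixed days, the 362 mL already contains that spread, and adding it again counts it twice.

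**Scale against the pilot's own uncertainty.** An SD of 362 mL from 20 women has a 95% interval, under normality, of 362 × √(19/32.85) to 362 × √(19/8.91), or about 275 to 529 mL. The worst-corner 381 mL lies well inside it. Knowing the pilot's hematocrit day would do little to narrow that range.

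**Which value the text points to.** Of the three scheduled hematocrits, one is before surgery, one is at placental delivery and one is on day 1. Only the last is after surgery, which fits the before-and-after description in Specific Aim 1. The Protocol (Protection Against Maternal Risk) also says study samples are taken together with clinical draws whenever possible, so the day 1 study value and the chart value may be the same specimen. Table 2 is credited to a previously published method, and discharge may be a label carried over from it. That last point is an inference.

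**The case for a change.** The strongest counter-argument is that Step 4 is more than a label. It assumes a blood volume at a stated time, and if volume on day 1 were still above the non-pregnant level, the formula would misstate the loss. If the volume at the draw is cV, then L = 1.5V(1 − 1/c) + B/c for a true loss B. A true difference of 205 mL would read 205/1.05 = 195 mL for a 5% excess in both arms, or 205/1.10 = 186 mL for 10%. A 2% excess in one arm only would move the difference by 0.02 × (1.5V − 2224), or 58 to 82 mL, in either direction.

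The algebra is right, but it tests the accuracy of the assumed volume. The same error could be present at discharge, so naming the day would not remove it. The documents give no volume data and no discharge day, and they do not indicate an imbalance between arms. Step 4 also attributes the return of volume to the hemorrhage itself, a mechanism that does not exclude day 1. An equal excess shrinks a real difference toward zero and does not create a false one.

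What stands is narrower. The readable text does not say which postoperative hematocrit enters Step 4, or which one produced the pilot figures. A reader who wants to recompute the outcome exactly needs that information, which a report of the results can supply.

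**Conclusion.** The mismatch in wording is real, but no change to the plan follows. The readable schedule leaves one postoperative draw as the natural closing value. The timeline figure that may confirm this is missing from the available text, so its content cannot be counted as absent from the plan. An analyst would use one time point for all women, and the comparison between arms is then unaffected: no bias is shown, no power is lost, and 50 per arm with 80.1% power reproduces. Only mixing of sources would cost power, at most 4.3 percentage points (80.1% to 75.8%) under assumptions the documents do not support. This conclusion rests on two conditions: that the same time point is used in both arms, and that any error in the assumed blood volume does not differ between arms.
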